10.5 REPORTING SAES TO HEALTH AUTHORITIES AND IECs/IRBS

The Sponsor will inform the relevant health authorities of any reportable SAEs according to the local regulatory requirements. Reporting to the health authorities will be according to the Reporting procedure.

The Sponsor will notify the Investigators in writing of the occurrence of any reportable SAEs. The Sponsor will be responsible for informing the IECs or IRBs that reviewed the clinical study protocol.

11 DATA COLLECTION AND MANAGEMENT

11.1 DATA COLLECTION AND ELECTRONIC CASE REPORT BOOK COMPLETION

Individual safety diary cards, specifically designed for this study by the Sponsor and provided to the study sites, will be given to study participants for the recording of daily safety information as described in [Section 9.1.3](#). These diary cards will include prelisted terms and intensity scales (see [Table 1](#) and [Table 2](#)) as well as areas for free text to capture additional safety information or other relevant details. Subjects will also be provided with rulers for measuring the size of injection site reactions, and with standard digital thermometers for measuring daily temperatures. To ensure consistency of reporting, the study sites will instruct subjects on how to correctly use these tools.

At specified intervals, the Investigator or an authorized designee will interview the subjects to collect the information recorded in the diary card, and will attempt to clarify anything that is incomplete or unclear. All clinical study information gathered by the study site will be reported electronically by the Investigator or authorized designee using a web-based CRB. (Any information that was not documented in the diary card will first be captured in the source document and then reported electronically.) The CRB has been designed specifically for this study under the responsibility of the Sponsor, using a validated Electronic Records/Electronic Signature-compliant platform (21 CFR Part 11).

To ensure the correct and consistent completion of the CRB, the Sponsor or authorized representative will provide all necessary tools, instructions, and training to all site staff involved in data entry prior to study start. Additional instructional documents such as training manuals and completion instructions will be provided to assist with data entry during the course of the study.

Upon completion of training, each user requiring access to the EDC system will be issued a unique username and password. In the event of a change in study personnel, each newly assigned individual will receive a unique username and password; the username and password of a previous user may not be reissued. If any study personnel leave the study, the Investigator is responsible for informing the Sponsor immediately so that their access is deactivated. An audit trail will be initiated in the EDC system at the time of the first data entry in order to track all modifications and to ensure database integrity.

The Investigator is responsible for the timeliness, completeness, and accuracy of the information in the CRBs; must provide explanations for all missing information; and must sign the CRB using an e-signature.

11.2 DATA MANAGEMENT

Management of SAE

During the study, SAE data (reported on the AE, Death, and Safety Complementary Information CRFs) will be integrated into the Sponsor's centralized GPE database upon receipt of these forms

and after a duplicate check. Each case will be assigned a case identification number. Each case will be assessed by the case management platform or its delegate before being reported to the relevant authorities as necessary. The assessment of related cases will be done in collaboration with the Clinical Study Director of Sanofi, the Pharmacovigilance Global Safety Expert and the RMO of Sanofi Pasteur. Follow-up information concerning a completed case will be entered into the GPE database, and a new version of the case will be created.

The information from the GPE database cases will be reconciled with that in the clinical database.

Management of Clinical and Laboratory Data

Clinical data, defined as all data reported in the CRB, and laboratory data will be handled by the Sponsor's Clinical Data Management (CDM) platform or authorized representative.

During the study, clinical data reported in the CRBs will be integrated into the clinical database under the responsibility of the Sponsor CDM platform. Data monitoring at the sites and quality control in the form of computerized logic and/or consistency checks will be systematically applied in order to detect errors or omissions. In addition, data reviews may be performed several times by the Sponsor's staff in the course of the study. Any questions pertaining to the reported clinical data will be submitted to the investigator for resolution using the EDC system. Each step of this process will be monitored through the implementation of individual passwords to maintain appropriate database access and to ensure database integrity.

The validation of the immunogenicity data will be performed at the laboratory level following the laboratory's procedures. Information from the laboratory will be checked for consistency before integration into the clinical Datawarehouse.

After integration of all corrections in the complete set of data, and after the SAE information available from CDM and the GPE Department has been reconciled, the database will be released for statistical analysis.

11.3 USE OF COMPUTERIZED SYSTEMS

The complete list of computerized systems used for the study is provided in a separate document which is maintained in the Sponsor trial master file.

11.4 DATA REVIEW

A blind review of the data is anticipated through the data review process led by Data Management before database lock.

12 STATISTICAL METHODS AND DETERMINATION OF SAMPLE SIZE

12.1 STATISTICAL METHODS

Clinical database data will be analyzed under the responsibility of the Biostatistics platform of the Sponsor, with the SAS software, at least version 9.4 (SAS Institute, Cary, North Carolina, USA).

A statistical analysis plan (SAP) will be written and peer reviewed before the database lock. In accordance with the protocol, the SAP will describe all analyses to be performed by the Sponsor and all the conventions to be taken.

12.1.1 Hypotheses and Statistical Methods for Objectives

12.1.1.1 Hypotheses

Safety

No hypotheses are to be tested.

Immunogenicity

No hypotheses are to be tested.

12.1.1.2 Statistical Methods

Safety

Safety results will be described for subjects in safety analysis set who received QIV-HD IM, QIV-HD SC, or QIV-SD SC. Solicited reactions (solicited injection site and systemic reactions), unsolicited AEs, SAEs, and AESIs will be summarized. The main parameters will be described with 95 % CI based on the Clopper-Pearson method (14).

- Unsolicited systemic AEs occurring within 30 minutes of injection (immediate unsolicited AEs)
- Solicited injection site reactions (pain, erythema, swelling, induration, and bruising) occurring within 7 days after the day of injection (D0 to D7) according to presence, time to onset, number of days of occurrence, maximum intensity (Grade 1, Grade 2, or Grade 3) and action taken. When more than 1 intensity level is reported within a time period, the highest intensity will be used.
- Solicited systemic reactions (fever, headache, malaise, myalgia, and shivering) occurring within 7 days after the day of injection (D0 to D7) according to presence, time to onset, number of days of occurrence, maximum intensity (Grade 1, Grade 2, or Grade 3) and

action taken. When more than 1 intensity level is reported within a time period, the highest intensity will be used.

- Unsolicited AEs occurring within 28 days after the day of injection by system organ class (SOC) and PT, time to onset, duration, maximum intensity (Grade 1, Grade 2, and Grade 3), and relationship to vaccination (for systemic AEs only).
- All SAEs that occur throughout the study by SOC and PT, time to onset, seriousness criteria, outcome and relationship to vaccination.
- All AESIs reported throughout the study by SOC and PT and relationship to vaccination.

Immunogenicity

Immunogenicity in terms of GMTs, seroconversion, and seroprotection rates will be summarized for each strain. The 95% CIs for the GMTs will be calculated using normal approximation of log-transformed titers. The GMT ratios of each QIV-HD group (IM or SC) to QIV-SD group will be obtained between groups with the 95% CIs calculated using normal approximation of log-transformed titers. The 95% CIs for the proportions will be based on the Clopper-Pearson method. The differences in the seroconversion rates between each QIV-HD group (IM or SC) and QIV-SD group will be computed along with the 2-sided 95% CIs by the Newcombe-Wilson method without continuity correction (15). In addition, the immunogenicity analyses will be performed by subgroups of age (<75, ≥75), and sex (male, female). Additional parameters may be displayed as appropriate. Details of the above analyses will be described in the SAP.

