5.1.2 Justification of the Study Design

The objectives of QHD00008-DFI15130 will be to assess the safety and immunogenicity (as assessed by HAI GMTs and seroconversion rates at 28 days post-vaccination) of QIV-HD when administered SC and IM compared with the local QIV-SD.

The control product is the local QIV-SD because it is the only seasonal influenza vaccine licensed in Japan.

In addition, the route of administration of seasonal influenza vaccine is SC in Japan, whereas IM in the US and Canada. Therefore, the QIV-HD will be administered by SC or IM method in this study.

The investigational QIV-HD has never been administered to Japanese subjects. However, given the acceptable safety data generated from the millions of doses of TIV-HD administered in the US and Canada and the fact that no changes will be made to the drug substance manufacturing process of QIV-HD compared to the TIV-HD process currently licensed in the US and Canada, the Sponsor considers that the risk/benefit ratio is appropriate for the conduct of a Phase I/II clinical study with QIV-HD with a small group included for an early safety data review.

Given the different volumes and administration routes of the QIV-HD and the local QIV-SD vaccines, QHD00008-DFI15130 will be a modified double-blind study in which only a designated administrator at each study site will know which vaccine has been administered to the subjects. The subjects and the Investigator/Sub-investigator in charge of the safety assessment will be blinded in order to decrease the potential bias in safety assessment.

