6.5 RANDOMIZATION AND ALLOCATION PROCEDURES

For the randomization of dose numbers, the sponsor or designee will supply a computer generated randomization list, which will be used for the labeling and packaging.

For Cohort 1, subjects who meet the inclusion/exclusion criteria and sign the ICF (subjects aged 65 years and older) will be randomly assigned to one of 2 study groups (QIV-HD by IM route or QIV-HD by SC route) in a 1:1 ratio by block randomization.

On the day of enrollment for Cohort 2 subjects, those subjects who meet the inclusion/exclusion criteria and sign the ICF (subjects aged 65 years and older) will be randomly assigned to one of 3 study groups (QIV-HD by IM route, QIV-HD by SC route, or QIV-SD by SC route) in a 1:1:1 ratio by block randomization, stratified according to age (<75, ≥75), sex, and site.

Site staff will connect to the IRT, enter the identification and security information, and confirm a minimal amount of data in response to IRT prompts. The IRT will then provide the vaccine dose number and have the site administrator confirm it. Dose numbers will be recorded on the source documents and CRBs. The full detailed procedures for group allocation are described in the IRT operation manuals. If the subject is not eligible to participate in the study, then the information will only be recorded on the screening/enrollment log.

Subject numbers that are assigned by the IRT will consist of a 12-digit string (a 3-digit country identifier, a 4-digit study center identifier, and a 5-digit subject identifier). For example, Subject 392000100005 is the fifth subject enrolled in Center Number 1 in Japan (392 being Japan country code).

Subject numbers should not be reassigned for any reason. The randomization codes will be kept securely in the IRT and an internal system.

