For Cohort 1, interactive response technology (IRT) will be used to assign subjects to one of 2 study groups (QIV-HD by IM route or QIV-HD by SC route) and to assign subject numbers in each of the groups. However, the randomization will be performed without stratification.

For Cohort 2, IRT will also be used to assign subjects to one of 3 study groups (QIV-HD by IM route, QIV-HD by SC route, or QIV-SD by SC route) and to assign subject numbers in each of the groups. The randomization will be stratified by value of age (<75, ≥75), sex (Male, Female), and sites.

Electronic data capture (EDC) will be used for the collection of data.

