In this study, QIV-HD will be compared to a local QIV-SD, and it is possible that the two vaccines contain different strains based on comparison of strains between Sanofi Pasteur QIV-HD (based on WHO / VRBPAC recommendations) and a local QIV-SD (based on NIID). Sanofi Pasteur plans on performing the HAI testing using both the QIV-HD and QIV-SD strains as test antigens for all the subjects, irrespective of the vaccine received. For example, if QIV-HD is comprised of a, b, c and d strains and QIV-SD is comprised of a, b, c and “d-like” strains (3 common and 1 “-like strain”), the proposed testing strategy would require HAI testing of sera from all subjects (irrespective of the vaccine received) with a, b, c, d and “d-like” strain test antigens in order to evaluate the comparability between the “-like strains” in this study.

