#### 2.4.5 Analyses of immunogenicity data

QIV-HD vaccine and QIV-SD vaccine contain the following strains:

	QIV-HD	QIV-SD
H1N1	A/Michigan/45/2015(H1N1)	A/Singapore/GP1908/2015(IVR-180)(H1N1)pdm09
H3N2	A/Hong Kong/4801/2014(X-263B)(H3N2)	A/Hong Kong/4801/2014(X-263)(H3N2)
B (Yamagata lineage)	B/Phuket/3073/2013	B/Phuket/3073/2013
B (Victoria lineage)	B/Brisbane/60/2008	B/Texas/2/2013

For the purposes of this section, the 7 virus strains in the vaccine groups will be labeled as follow:

- A/Michigan/45/2015(H1N1) A1
- A/Singapore/GP1908/2015(IVR-180)(H1N1)pdm09 A1-like
- A/Hong Kong/4801/2014(X-263B)(H3N2) A2
- A/Hong Kong/4801/2014(X-263)(H3N2) A2-like
- B/Phuket/3073/2013 B1
- B/Brisbane/60/2008 B2
- B/Texas/2/2013 B2-like

The immunogenicity analyses will be performed on the PPAS and the FAS. The main immunogenicity analyses will be conducted on Cohort 2 for the PPAS. Similar analyses with the main immunogenicity analyses will also be conducted on Cohort 2 for the FAS and Cohort 1+Cohort 2 for PPAS and FAS, unless otherwise specified.

For descriptive purposes, no hypothesis will be tested.

Assuming that  $\log_{10}$  transformation of the titers/data follows a normal distribution, at first, the mean and the 95% CI will be calculated on  $\log_{10}$  (titers/data) using the usual calculation for normal distribution (using Student's  $t$  distribution with  $n-1$  degree of freedom) as described in [Section 2.5.8.1](#) and [Section 2.5.8.2](#), then antilog transformations will be applied to the results of calculations, in order to provide GMs and their 95% CI.

For categorical data such as seroprotection and seroconversion, the percentage of subjects achieving the endpoint and the corresponding 95% CIs (Clopper-Pearson method) (2) will be performed for pre-vaccination (V1) and post-vaccination immunogenicity (V3) (See the detail in [Section 2.5.8.3](#)). The 95% CI of the difference in percentage between time points and vaccine

group will be computed using the Wilson score method without continuity correction, quoted by Newcombe (3) (See the detail in [Section 2.5.8.4](#)).

For GMTs of HAI, the following will be analyzed by vaccine groups and strains.

- GMTs of HAI for QIV-HDs and QIV-SD, and the ratio of GMTs of HAI for each QIV-HD/QIV-SD at V3 after vaccination
- GMTs of HAI for QIV-HDs and QIV-SD using strains selected for each vaccine, and the ratio of GMTs of HAI for each QIV-HD/QIV-SD at V3 after vaccination

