- Ratio of GMTs of HAI for QIV-HDs between the 2 different administration routes at V3 after vaccination

GMTs of HAI for each vaccine group at V1 and V3 after vaccination and the corresponding ratio of GMT will be summarized by strains.

For seroconversion rates, the following will be analyzed by vaccine groups and strains.

- Seroconversion rates and the difference of each QIV-HD and QIV-SD (QIV-HD – QIV-SD) at V3 after vaccination
- Seroconversion rates using strains selected for each vaccine and the difference of each QIV-HD and QIV-SD (QIV-HD – QIV-SD) at V3 after vaccination
- Seroconversion rates and the difference of QIV-HDs between the 2 different administration routes at V3 after vaccination

For seroprotection rate, the following will be analyzed by vaccine groups and strains

- Seroprotection rates of HAI for QIV-HDs and QIV-SD at V3 after vaccination
- Seroprotection rates of HAI for each vaccine group at V1 and V3 after vaccination

Immunogenicity data will be analyzed using GMTs, seroconversion rate, and seroprotection rate at each time point by following subgroups:

- Age: 65-<75 and  $\geq 75$  years
- Sex: Male and Female
- Previous influenza vaccination status: Yes and No
- Baseline seropositivity status:  $<10$  [1/dil] and  $\geq 10$  [1/dil]

For comparison between groups in terms of GMTs, the exploratory analyses will be performed if necessary.

The followings will be presented as the summary of HA antibody response for each antigen:

- The number of subjects with HAI titer  $<10$  [1/dil] and  $\geq 10$  [1/dil], the number of subjects with seroprotection ( $\geq 40$  [1/dil]), and summary of titers [1/dil] (using geometric mean and the corresponding 95% CI, median, minimum and maximum value of antilog transformed value, and mean and standard deviation calculated on  $\log_{10}$  (titers/data)) at V1 and V3

- GMTR of the individual titers (using geometric mean and the corresponding 95% CI, median, minimum and maximum of antilog transformed value, and mean and standard deviation calculated on  $\log_{10}$  (titers/data)) at V3 over V1, and the number of subjects with seroconversion at V3

In addition, Reverse Cumulative Distribution Curve (RCDC) by vaccine groups and timepoints (V1 and V3) will be presented in a graph for each strain in Cohort 2 for the PPAS and FAS.

Individual diagram of titers will be also presented for each strain by vaccine groups in Cohort 2 for the PPAS.

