### 2.5.8.2 Confidence interval for the GMT ratio between 2 groups

The calculations of the 95% CI for the GMT ratio between 2 groups are as following:

Logarithmic transformation of the individual titers will be calculated first. Assuming that individual  $\log_{10}(\text{titer})$  is normally distributed, the 95% CI for the difference in  $\log_{10}(\text{GMT})$  between group  $i$  and group  $j$  will be in the form:

$$\bar{X}_i - \bar{X}_j \pm t(1 - \alpha/2, n_i + n_j - 2) \cdot S \sqrt{1/n_i + 1/n_j}$$

where  $\bar{X}_i = \log_{10}(\text{GMT})$  is the mean of  $\log_{10}(\text{titer})$  of group  $i$ ,

$S^2 = [(n_i - 1)S_i^2 + (n_j - 1)S_j^2] / (n_i + n_j - 2)$  is the pooled sample variance,

$n_i$  and  $S_i^2$  are the sample size and sample variance of group  $i$ ,

$t(1 - \alpha/2, n_i + n_j - 2)$  is the  $100(1 - \alpha/2)$  percentile of the  $t$ -distribution with degrees of freedom (df) =  $n_i + n_j - 2$ .

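### The between-group GMT ratios are valid but unadjusted; a prespecified same-antigen ratio adjusted for D0 titer and the randomisation strata, reported alongside, is a cheap improvement

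*Protocol*

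**What the plan says.** Protocol 12.1.1.2 states that "The GMT ratios of each QIV-HD group (IM or SC) to QIV-SD group will be obtained between groups with the 95% CIs calculated" by normal approximation on log titers, and names no covariate. SAP 2.5.8.2, which begins "The calculations of the 95% CI for the GMT ratio between 2 groups are as following", gives a difference of two mean log10 titers with a variance pooled over the two groups and n_i + n_j − 2 degrees of freedom. SAP 2.4.5 plans this for each QIV-HD/QIV-SD ratio and adds an IM/SC ratio for QIV-HD.

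The candidate covariates are already in the plan:

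- **D0 titer.** Protocol 5.1.3 plans a pre-vaccination sample for every subject. SAP 2.1.5 plans on "performing the HAI testing using both the QIV-HD and QIV-SD strains as test antigens for all the subjects", so a D0 titer to the same antigen is due in all three arms.
- **Strata.** Protocol 6.5 allocates Cohort 2 "in a 1:1:1 ratio by block randomization, stratified according to age", sex and site. SAP 1.1 agrees: "The randomization will be stratified by value of age (<75, ≥75), sex (Male, Female), and sites".

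On further comparisons, SAP 2.4.5 says only: "For comparison between groups in terms of GMTs, the exploratory analyses will be performed if necessary". It gives no model, covariate or trigger.

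**The concern.** The formal objective is descriptive (Protocol section 2, SAP 1.2). Protocol 5.1.2 nevertheless puts the purpose as assessing safety and immunogenicity "of QIV-HD when administered SC and IM compared with the local QIV-SD", and Protocol 1.4 says the same. With no hypothesis test and no power calculation, the GMT ratio and its interval are among the outputs that carry this comparison, so their precision matters.

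Two things are at stake. If D0 titer predicts V3 titer, leaving it out makes the interval wider than it need be. If D0 GMTs differ by chance between arms of 55, part of that difference carries into the V3 ratio. An adjusted ratio chosen after the key codes are released (SAP section 4) would be post hoc. Stratified blocks already largely balance age, sex and site, so nearly all the protection would come from D0.

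**Working it through.** **Inputs from the documents.** 55 per arm in Cohort 2 (SAP 1.3); two-sided 95% interval (SAP 2.5.8.2); about 2 sites, so 1 df for site (Protocol section 3); values below 10 set to LLOQ/2 = 5 (SAP 2.5.3.1); missing immunogenicity data expected to be at most 5% (Protocol 12.3.2).

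**Assumptions, not in the documents.** Log10 SD 0.5 (range 0.4 to 0.6); D0-to-V3 correlation 0 to 0.7. The plan states no interval width, so there is no figure to reproduce.

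**1. Unadjusted interval (SAP 2.5.8.2).** Half-width = t(0.975, 108) × SD × √(2/55) = 1.982 × 0.5 × 0.1907 = 0.189 log10. The ratio is multiplied and divided by 10^0.189 = 1.545 (1.42 at SD 0.4, 1.69 at SD 0.6).

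**2. Adjusted interval, model-based.** One three-arm fit, N = 165, with k = 4 covariate df (D0, age, sex, site) and 165 − 3 − 4 = 158 residual df. Expected half-width = t(0.975, 158) × SD × √(1 − R²) × √(1 + k/(N − 4 − k)) × √(2/55), where t = 1.975 and √(1 + 4/157) = 1.0127.

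| R | CI factor | log width against unadjusted |
|---|---|---|
| 0 | 1.551 | × 1.009 |
| 0.3 | 1.520 | × 0.96 |
| 0.5 | 1.463 | × 0.87 |
| 0.7 | 1.368 | × 0.72 |

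Break-even is R = 0.13. These are expected widths. In simulated single trials at correlation 0, the 97.5th percentile of the width ratio was about 1.10.

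**3. Choice of standard error.** A three-arm fit pools variance over all arms, where SAP 2.5.8.2 pools only the two compared. With assumed SDs of 0.6, 0.6 and 0.4 (QIV-SD smallest), 25% of D0 below 10 and correlation 0.3, 0.5, 0.7, simulated coverage of the IM/SC interval was 92.0, 92.3 and 93.1% with model-based errors, and 94.6, 95.0 and 95.3% with HC3. With equal SDs and no floor, the HC3 width was × 1.02, 0.98, 0.89 and 0.74 at correlation 0, 0.3, 0.5 and 0.7.

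**4. D0 values below 10.** With model-based errors, the simulated width was × 0.96, 0.88, 0.75 with 25% below 10, and × 0.97, 0.90, 0.79 with 50% below 10, at latent correlation 0.3, 0.5, 0.7.

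**5. Missing D0.** Protocol 5.1.4 still vaccinates a subject after three failed draws, and neither FAS nor PPAS requires a D0 titer. 5% of 55 is 2.75, so take 3 missing per arm. With 52 adjusted against 55 unadjusted, the model-based width is × 1.04, 0.99, 0.90 and 0.74 at R 0, 0.3, 0.5 and 0.7, with break-even R = 0.27. With HC3 as well, the simulated median was × 1.055, 1.03, 1.01, 0.92 and 0.75 at correlation 0, 0.2, 0.3, 0.5 and 0.7.

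**6. Chance D0 imbalance.** Its 95% limit between two arms is 10^(1.96 × 0.5 × 0.1907) = 10^0.187 = 1.54-fold. The shift carried into the V3 ratio is 10^(0.187 × r): 1.14, 1.24 and 1.35-fold at r = 0.3, 0.5 and 0.7. An imbalance above 1.25-fold in either direction has probability 31% per pair. The floor reduces the shift. A width of × 0.79 in step 4 implies an effective R of about 0.62, and 10^(0.187 × 0.62) is about 1.3-fold.

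**The case against.** The strongest reply is that nothing is wrong. The study is descriptive, the unadjusted interval already allows for chance D0 imbalance, and simulated coverage was about 95% for both intervals when arm SDs were equal. This stands, and it is why the unadjusted ratio should remain the main result. A reader might infer that omitting the stratification factors or baseline invalidates the planned intervals. The documents do not support that: randomisation justifies the unadjusted comparison, and no test or decision rule depends on it.

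Second, the plan does use baseline. SAP 2.4.5 gives V1 and V3 GMTs, the within-subject GMTR, seroconversion differences, reverse cumulative distribution curves and subgroups by baseline seropositivity. A reader could see an imbalance there. But none of these adjusts the ratio, and no between-group ratio of GMTRs is specified.

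Third, the benefit depends on a correlation that the documents do not give. This also stands. A reader might infer that adjustment always narrows the interval, or that the 0.9% average widening at R = 0 is the most it can cost. Neither holds. Break-even moves with the fit, HC3 and missing D0 both add width, and a single trial can come out about 10% wider.

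Fourth, age, sex and site add little protection. That is true; they cost 3 df and make the model match the randomisation.

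**Conclusion.** The point holds as a cheap improvement, not an error. Every between-group GMT ratio in the plan is unadjusted, the covariates are already collected, and the open exploratory line in SAP 2.4.5 does not supply a prespecified alternative.

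The size rests on assumptions outside the documents (log10 SD 0.5, 55 per arm, no D0 floor). With HC3, the gain in log width is about 2% at correlation 0.3, 11% at 0.5 and 26% at 0.7, against an average loss of 2 to 3% at correlation 0. Many D0 titers below 10 would reduce the gain. With about 5% lacking D0, there is none on average at correlation 0.3 or less. The protection against imbalance is the other half of the case. The shifts of 1.14 to 1.35-fold belong to an imbalance at its 95% limit, not a typical one, and are upper figures because the floor lowers them.

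**What to change.** Before database lock, add to SAP 2.4.5 and 2.5.8.2, for Cohort 2 only (Cohort 1 has no QIV-SD arm and was not stratified):

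- For each antigen, fit one three-arm linear model of log10 V3 titer on vaccine group, log10 V1 titer to the same antigen (values below 10 at LLOQ/2), age stratum, sex and site, with HC3 standard errors.
- Report the adjusted ratio and 95% CI beside the unadjusted ratio, which stays the main result if the two differ.
- Leave out the ratio described as "GMTs of HAI for QIV-HDs and QIV-SD using strains selected for each vaccine". There the D0 antigen would differ between arms for H1N1, H3N2 and B/Victoria.
- Report the number of subjects dropped for missing D0 and the share of D0 titers at the LLOQ/2 floor.
- Record the addition in SAP 1.6, which now has no entry.

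The cost is SAP text and 7 antigens × 2 analysis sets (PPAS and FAS) = 14 fits, each giving both QIV-HD/QIV-SD ratios and the IM/SC ratio. No new data are needed. The downsides are a few degrees of freedom, about 2% in width for HC3 when arm SDs are equal, loss of subjects without D0 from the adjusted ratio only, and a second estimate per antigen to explain.
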